5.1. Inclusion Criteria

Participants are eligible to be included in the study only if all of the following criteria apply:

Age

1. Participant must be between 30 days and 120 days of age (inclusive), at the time of enrollment (study Day 1)

Type of Participant and Disease Characteristics

- 2. Hospitalized for acute non-surgical illness
- 3. Completed acute stabilization phase of treatment, including fluid rehydration and antibiotic course, prior to enrollment (study Day 1)

Weight

4. WAZ at enrollment (study Day 1) is less than negative 2 (<-2)

Sex

5. Any

Informed consent

6. Participant's parent(s)/legal guardian is capable of giving informed consent which includes agreement to comply with the requirements and restrictions listed in the informed consent form (ICF) and in this protocol

Additional requirements

- 7. Participant's parent(s)/legal guardian agrees to stay in contact with the study site for the duration of the study, provide updated contact information as necessary, and have no current plans to relocate from the study area for the duration of the study
- 8. Participant's parent(s)/legal guardian has easy access to reliable refrigeration (for storage of investigational product)
- 9. Participant receives some feedings from breastmilk and mother intends to continue breast-feeding.

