9.4. Primary Statistical Hypotheses and Sample Size Determination

The primary study hypothesis is that the difference in the mean change from baseline in WAZ is larger for participants randomized to at least 28 days of Bi-26 relative to placebo.

For the sample size calculation for the primary hypothesis, it is assumed that the between_group difference in the WAZ change from baseline is 0.45 with a standard deviation of 1.3. Based on the above assumption(s) using a 2-sided alpha of 5% and a power of at least 90%, a total of 354 participants, 177 in each group, is required.

Assuming a 10% loss to follow-up and a 3% mortality rate, a sufficient number of participants will be screened to ensure approximately 396 randomly assigned participants are enrolled, 198 in each treatment group.

Figure 2: Sample size sensitivity

N/group, 1-sided α =2.5%, Power=90%

9.5. **Populations for Analyses**

For purposes of analysis, the following populations are defined:

- Intention-to-treat (ITT) population: All participants randomly assigned to study intervention.
- **Modified intention-to-treat (mITT) population**: All participants randomly assigned to study intervention, who received at least one dose (including a partial dose) of the study intervention. Participants will be analyzed according to the intervention they were randomized.
- **Per-Protocol (PP) population**: All participants randomly assigned to study intervention, who received the study intervention, have a Day 90 visit, and did not substantially deviate from the protocol procedures. Participants will be analyzed according to the intervention they actually received. Details of criteria for defining the PP population will be specified in the Statistical Analysis Plan (SAP). The inclusion of participants in the PP population will be determined prior to unblinding the study. A participant data listing and a table with protocol deviations will be presented.
- **Safety population**: All participants randomly assigned to study intervention, who received any dose, including a partial dose, of the study intervention. Participants will be analyzed according to the intervention they actually received.

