9.6. Statistical Analyses

The principal features of the statistical analysis are described in this section. A more technical and detailed document of the features will be found in a separate SAP, which is to be finalized before unblinding of the study. When the study is completed and the data are collected, a blinded review of the planned analysis will be carried out. The review will look at the definition of outliers, violators, and exclusion of participants or data from the analysis sets. Decisions made based on the review will be documented.

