6 STUDY OBJECTIVES AND ENDPOINTS

6.1 Primary Objective

Table 1. Primary objective

Objective		Estimand	
To evaluate the change in weight (standardized for age) of infants	a)	Population : The Modified Intent to Treat (mITT) population will be used for the analysis.	
receiving Bi-26	b)	Endpoint : Weight-for-age z-score (WAZ) change from baseline (CFB) (Day 1) to the Day 56 visit in Bi-26 group.	
	c)	Population level summary : Mean change from baseline in WAZ in the Bi-26 group compared to placebo with stratification blocking factors and feeding regimen covariate(s).	
	d)	Intercurrent event(s) : Including but not limited to treatment discontinuation.	

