7.2 Randomization and blinding

Randomization: On the day of hospital discharge (Visit 1, Day 1) participants will be randomized 1:1 to receive either Bi-26 or placebo. To minimize differences between Bi-26 and placebo groups within a given treatment arm, randomization will be stratified by:

- 1. Country (Bangladesh, Kenya, Pakistan, Tanzania)
- 2. Age at enrollment (Study Day 1):30 to 59 days of age, 60 to 120 days of age
- 3. Discharge destination (home, nutritional rehabilitation unit)
- 4. WAZ (< -3 versus > -3)

Dynamic randomization will be utilized to balance the treatment groups across the study population, site level, stratum level, and within stratification factors. Target randomization is approximately 2/3 of participants with WAZ between -2 and -3 and approximately 1/3 with WAZ \leq -3. The distribution of participants in WAZ strata will be monitored throughout the study in order to determine if a stratum needs to be temporarily/permanently closed for enrollment.

See Sections 11.5.1 and 11.6.6 for the calculations of age and WAZ to be used for stratification, respectively.

Confidential Page 15 of 50

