10.2 Baseline Definition

Baseline is defined as the last available value prior to the participant receiving the first dose of the study intervention. If the potential Baseline ACR is on Day 1 (and time is not recorded), it is assumed that the ACR occurred before the first dose of the study intervention was received.

CFB is calculated as:

$$CFB = Observed\ value - Baseline\ Value$$

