10.3.3 Missing Efficacy data

Missing efficacy data will not be imputed.

Confidential Page 23 of 50

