11.5.2.1 Analysis of endpoint

WAZ will be summarized using descriptive statistics for actual and CFB values by visit and treatment group.

A MMRM will be used to estimate the difference in mean CFB between Bi-26 and Placebo, adjusting for covariates baseline WAZ, age (in days), country and discharge destination. The model will use CFB in WAZ as outcome and include the following effects:

- Fixed effects: Treatment, Visit (categorical), Treatment*Visit interaction, WAZ at baseline (continuous), Age (in days) at baseline, Country, Discharge destination
- Random intercepts: participant.

and will be fit using data from all planned follow-up visits where WAZ was measured, ie, Day 28, 56, and 90 visits. The adjusted interaction effects (Treatment*Visit) will be presented as estimates of the difference in CFB between treatment groups at each follow-up visit (Day 28, 56, and 90). The associated 95% CIs and p-values will be presented. PROC MIXED will be used to fit the models. SAS code for the models is provided in Appendix 3. If the WAZ score is not normally distributed, an appropriate transformation, such as the natural log, will be used as outcome for analysis. Normality will be investigated using q-q plots.

A participant listing of WAZ will be presented with actual values and CFB.

The descriptive table, model and listing will use the mITT population. The summary table will be repeated for the PP population.

Line graphs with the means and 95% CIs for WAZ will be presented by treatment group for visits Baseline, 28, 56, and 90.

Confidential Page 32 of 50

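### The non-normality fallback replaces the primary outcome with a transformation; the only one named, the natural log, is undefined for most WAZ and many change-from-baseline values

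*SAP*

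**What the plan says.** The primary estimand in SAP 6.1 is "Mean change from baseline in WAZ in the Bi-26 group compared to placebo". SAP 11.5.2.1 fits a mixed model to CFB in WAZ at Days 28, 56 and 90, adjusted for baseline WAZ, age, country and discharge destination. The same section then says: "If the WAZ score is not normally distributed, an appropriate transformation, such as the natural log, will be used as outcome for analysis". Normality is to be judged from q-q plots. The section gives no threshold for departure from normality, no visit, no shift constant and no way back to the original scale.

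Four other places bear on this:

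- Protocol 5.1 admits only infants with WAZ below -2 on Day 1.
- SAP 10.2 defines CFB as the observed value minus the baseline value, so it can be zero or negative.
- SAP 10.3.3 states: "Missing efficacy data will not be imputed".
- Protocol 9.6 provides for a blinded review of the planned analysis once the data are in, and describes its content as follows: "The review will look at the definition of outliers, violators, and exclusion of participants or data from the analysis sets".

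SAP 11.5.3.1 applies the same transformation rule to weight, the key secondary outcome.

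**The concern.** The rule replaces the primary outcome; it does not add a sensitivity analysis. This raises three problems.

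- **The named transformation fails.** A log of WAZ does not exist for any infant at entry, nor for any infant still at or below zero at follow-up. A log of CFB does not exist for any infant who has not gained. With no imputation, undefined values would leave the model according to the outcome, and at different rates in the two arms.
- **Any substitute is open.** The variable to transform, the function and the constant would all be chosen after outcome data exist. Whatever is chosen, the model no longer estimates the difference in mean WAZ change. Untransformed means by arm and visit would still be tabulated, but without adjustment.
- **The trigger names the wrong quantity.** Read literally, it tests the WAZ score and not the model residuals. Entry WAZ is cut off at -2, with a target of "approximately 2/3 of participants with WAZ between -2 and -3 and approximately 1/3 with WAZ" at or below -3, so it is skewed by design even if the residuals are normal.

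The weight analysis is less affected. Weight is always positive, so a log of weight loses nobody. But the text does not say whether weight or CFB in grams is to be transformed, and a log of weight would turn a difference in grams into a ratio.

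**Working it through.** **Inputs.** Protocol 9.4 assumes a "difference in the WAZ change from baseline is 0.45 with a standard deviation of 1.3", with two-sided alpha 5%, power of at least 90% and 177 infants per group. The documents give no placebo mean change, m. I assume 0 to 1.0 WAZ units, and normal CFB with SD 1.3 in both arms. The Bi-26 mean is m + 0.45.

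**1. The plan's own figure.** n per group = 2 × (1.960 + 1.282)² × 1.3² / 0.45² = 175.4, so 176. The t-test version gives 176.35, so 177. Power at 177 per group is 90.1%. The stated sample size is reproduced, on the untransformed scale.

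**2. Share with ln(CFB) undefined at Day 56.** P(CFB ≤ 0) = Φ(-mean/1.3), with counts out of 177.

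| Placebo mean m | Placebo | Bi-26 |
|---|---|---|
| 0 | 50.0% (88.5) | 36.5% (64.5) |
| 0.5 | 35.0% (62.0) | 23.2% (41.1) |
| 1.0 | 22.1% (39.1) | 13.2% (23.4) |

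At m = 1.5 the shares fall to about 12% and 7%.

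**3. Share with ln(WAZ) undefined.** At baseline it is 100%. At Day 56, WAZ above 0 requires CFB above 2, because baseline is below -2. Hence P(WAZ ≤ 0) is at least Φ((2 - mean)/1.3).

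| Placebo mean m | Placebo, at least | Bi-26, at least |
|---|---|---|
| 0 | 93.8% | 88.3% |
| 0.5 | 87.6% | 79.0% |
| 1.0 | 77.9% | 66.4% |

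**4. Effect of dropping infants with CFB ≤ 0.** The mean among those retained is mean + 1.3 × φ(mean/1.3)/Φ(mean/1.3). For m = 0 this is 1.037 on placebo and 1.219 on Bi-26, a difference of 0.18 where the true difference is 0.45. For m = 0.5 and 1.0 the difference is 0.23 and 0.28. So selection alone removes a large part of the effect before any log is taken. In 20,000 simulated trials, a Welch test on ln(CFB) among infants with CFB above 0 has power of 24%, 36% and 49% for m = 0, 0.5 and 1.0. The untransformed t test has 90%.

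**5. Shifted log, nobody dropped.** The outcome is ln(CFB - minimum + c), with m = 0.5; results at m = 0 and 1.0 are within half a percentage point.

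| c (smallest shifted value) | Power | Mean difference, log scale |
|---|---|---|
| 0.01 | 77% | 0.149 |
| 0.1 | 84% | 0.138 |
| 1 | 89% | 0.102 |
| 5 | 90% | 0.052 |

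The constant moves power by about 13 points and changes the estimate nearly threefold (0.149/0.052 = 2.9). None of these estimates is a difference in mean WAZ change.

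**6. The trigger.** Truncated normals on WAZ below -2, scaled so that one third lie at or below -3, have skewness -0.73, -0.99 and -1.23 for underlying means of -2.5, -2 and -1. An exponential tail gives -2.0. A q-q plot of entry WAZ would therefore be expected to depart from normality whatever the residuals do.

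The simulations compare the two arms at Day 56 only; they do not fit the full repeated-measures model.

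**The case against.** The strongest reply is that the SAP asks for an appropriate transformation and offers the log only as an example. A function that cannot be computed at baseline is not appropriate, and no competent analyst would drop up to half of the placebo arm. On that view the realistic case is a shifted log with a moderate constant, which costs little power. This is a fair point about emphasis: the plain-log losses show what the named option would do, not what is most likely to happen. But it concedes that the choice is open, and step 5 shows that the choice matters.

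Second, Protocol 9.6 promises a blinded, documented review of the planned analysis, and a transformation could be settled there. The documents do not assign the q-q check to that review, nor do they place it after unblinding; its timing is simply not stated. Blinding would limit selective choice, but it would not restore the estimand.

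Third, the WAZ score may be loose wording for the modelled outcome. That is possible, and the skewness in step 6 matters only if baseline WAZ is what gets plotted. The text does not say.

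Fourth, the SAP says that SAS code is in Appendix 3. It is not readable in the copy reviewed, so the statement that no alternative is fixed applies to the visible text.

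Finally, the rule may never be triggered. That limits how likely the harm is, but it is no reason to keep an unworkable rule on a Phase 3 primary endpoint.

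**Conclusion.** The concern holds, and the rule should be fixed before unblinding. This is a stated rule that fails on the trial's own data, not just a missing detail. The log is undefined for every entry WAZ and for every CFB of zero or less, and any non-linear transformation abandons the mean-change estimand. That the log fails, and that the estimand is lost, follow from the documents alone. The size of the effect rests on normal CFB with SD 1.3 and on an assumed placebo mean. The share with undefined ln(CFB) shrinks as the placebo gain rises or the SD falls. The harm is conditional on the fallback being used. The weight analysis has the milder problem of an unclear variable and a changed scale, with no loss of infants if weight itself is logged.

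**What to change.** Delete the transformation sentence in SAP 11.5.2.1 and its counterpart in 11.5.3.1. State that the mixed model on untransformed CFB is the primary analysis (WAZ) and key secondary analysis (grams) whatever the q-q plots show. Apply the plots to model residuals, not to WAZ or weight. If residuals are clearly non-normal, report one pre-specified sensitivity analysis that estimates the same difference in mean CFB, using an empirical sandwich standard error or a bootstrap confidence interval; name which in the SAP. A rank-based analysis may be added as supportive only, because it does not estimate mean change.

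Fixing the diagnostic, the function and the constant at the blinded review would remove the open choice, but it would still change the estimand, so deletion is the better remedy. The cost is two sentences of SAP wording and one sensitivity table. The 177 per group and the 90% power are unchanged.

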11.5.2.2 Subgroup analysis

Summary statistics may be presented by treatment and visit for subgroups as specified in Section 8.2 for WAZ. The mean difference in CFB with 90% confidence intervals between treatment and placebo will be presented at each visit.

A forest plot will be presented for selected subgroups showing the 90% CIs for mean CFB in WAZ at Day 56 visit by treatment group.

The mITT will be used for this analysis.

11.5.2.3 Association between study intervention compliance and CFB in WAZ

In order to evaluate the relationship between CFB in WAZ at Day 56 and study intervention compliance, the Pearson's and Spearman's correlations between CFB in WAZ at Day 56 and study intervention compliance will be presented by treatment group in a table. A scatter plot by treatment group will be presented with CFB in WAZ at Day 56 as the dependent variable and study intervention compliance as the independent variable. PROC CORR will be used to produce the correlations.

The same scatter plot with CFB in weight (grams) will also be presented. The mITT will be used for this analysis.

11.5.2.4 Sensitivity Analyses

11.5.2.4.1 Per Protocol population

As a sensitivity analysis, the same model presented in Section 11.5.2.1 will be presented for the PP population with corresponding results.

11.5.2.4.2 Adjustment for possible confounding variables

In order to quantify the impact of confounding factors, the same model presented in Section 11.5.2.1 will be adjusted for possible confounding factors that may include:

- study intervention compliance (see Section 11.4)
- proportion of breast milk feedings (see Section 11.4.2)
- infant concomitant antibiotic or probiotic use through the Day 56 visit (yes/no)
- primary place of storage (see Section 11.4.1).

For each of the confounders to be included in the analysis, the same model presented in Section 11.5.2.1 will be run adjusted by the confounder. If the p-value of the overall test for the confounder < 0.2 it will be included in the final model. The same estimates will be presented as for the primary efficacy analysis in a summary table.

Confidential Page 33 of 50

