7.1.3 Justification of Sample Size

[figure not shown]
The primary study hypothesis is that the difference in the mean change from baseline in WAZ is larger for participants randomized to at least 28 days of Bi-26 relative to placebo.

For the sample size calculation for the primary hypothesis, it is assumed that the between group difference in the WAZ change from baseline in 0.45 with a standard deviation of 1.3. Based on the above assumption(s) using a 2-sided alpha of 5% and a power of at least 90%, a total of 354 participants, 177 in each group are required.

Confidential Page 14 of 50

Assuming a 10% loss to follow-up and a 3% mortality rate, a sufficient number of participants will be screened to ensure approximately 396 randomly assigned participants are enrolled, 198 in each treatment group.

Figure 2. Sample size sensitivity

N/group, 1-sided $\alpha = 2.5\%$, Power=90%

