11.5.4 Secondary outcome: Change over time in WAZ by duration of dosing

11.5.4.1 Analysis of endpoint

The difference in the change over time will be represented as the estimated difference in CFB at Day 90 using the results generated by the model as described in Section 11.5.2.1 for the PP population.

In order to take duration of dosing into account, the model described above will be adjusted by study intervention compliance (see Section 11.4) and presented in separate tables for the mITT and PP populations.

11.5.5 Secondary outcome: Proportion of infants with increase in WAZ ≥ 0.3 , 0.4 and 0.5 at Day 56

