Appendix 3. Summary of Efficacy Analyses

Table 8. Analyses of Efficacy Parameters

Parameter	Population	Statistical Method	Missing Data	Interpretation
CFB in WAZ	mITT	MMRM	Observed cases	Primary analysis
CFB in WAZ	PP	MMRM	Observed cases	Sensitivity
CFB in WAZ	mITT, PP	MMRM adjusted for study intervention compliance	Observed cases	Secondary/Sensitivity
CFB in WAZ	mITT	MMRM with adjustment of confounding variables	Observed Cases	Secondary, Sensitivity
CFB in WAZ adjusted for gestational age	mITT	MMRM	Observed Cases	Sensitivity
CFB in Weight	mITT	MMRM	Observed cases	Key Secondary
Proportion of participants with increase in WAZ \geq 0.3, 0.4, 0.5 at Day 56	Safety, PP	Estimation of proportions with mid-P CIs and logbinomial regression to estimate risk ratio	Observed cases	Secondary, Sensitivity
Proportion of participants with WAZ > - 2	Safety, PP	Estimation of proportions with mid-P CIs and log-binomial regression to estimate risk ratio	Observed cases	Secondary, Sensitivity
Proportion of participants that were rehospitalized	Safety, PP	Neg-binomial model to estimate incidence rate ratio	Observed cases	Secondary, Sensitivity
Proportion of participants that were re-hospitalized	Safety, PP	Estimation of proportions with mid-P CIs and log-binomial model to estimate risk ratio	Observed cases	Secondary, Sensitivity

[figure not shown]
Confidential Page 48 of 50

Proportion of mITT, PP participants that had samples with presence of *B. infantis*

Estimation of proportions with mid-P CIs

Observed cases

[figure not shown]
Secondary, Sensitivity

[figure not shown]

Confidential Page 49 of 50

Page 50 of 50 Confidential

GF0015-MNK01-301 SAP

Gates MRI MNK01-301 SAP Vault eTMF Document Number: VV-TMF-47158 | 1.0

Signature Page for VV-TMF-47158 v1.0

Reason for signing: Approved	Name: Role: Biostatistics Date of signature: 15-Sep-2023 11:21:55 GMT+0000
Reason for signing: Approved	Name: Role: Clinical Development Date of signature: 15-Sep-2023 12:29:06 GMT+0000
Reason for signing: Approved	Name: Role: Biostatistics Date of signature: 15-Sep-2023 13:59:21 GMT+0000

Signature Page for VV-TMF-47158 v1.0

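### SAP 11.5.2.4.2 adjusts the treatment effect for post-randomisation variables labelled as confounders, so this sensitivity estimate can be biased for the total effect

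*SAP*

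**What the plan says.** SAP 11.5.2.4.2, under Sensitivity Analyses, sets out to quantify the impact of confounding on the primary result. It takes the mixed model of SAP 11.5.2.1 and adds candidates one at a time. The list is open (it gives factors that may be included) and names four: study intervention compliance, proportion of breastmilk feedings, "infant concomitant antibiotic or probiotic use through the Day 56 visit (yes/no"), and primary place of storage. The selection rule is "If the p-value of the overall test for the confounder < 0.2 it will be included in the final model". The same treatment estimates as in the primary analysis are then tabulated. SAP Appendix 3, Table 8 lists the result as "MMRM with adjustment of confounding variables", with a secondary and sensitivity role.

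The primary model in SAP 11.5.2.1 contains treatment, visit, their interaction, and four baseline or design covariates: baseline WAZ, age, country and discharge destination.

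For the change-over-time endpoint, SAP 11.5.4.1 says that "the model described above will be adjusted by study intervention compliance", with no p-value screen.

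**The concern.** A confounder of a randomised comparison would have to influence assignment, or be imbalanced before it. None of the four candidates can. Compliance accumulates over the treatment period (SAP 11.4), breastmilk share and antibiotic or probiotic use run to the Day 56 visit (SAP 11.4.2 and 11.5.2.4.2), and storage is recorded at treatment-phase visits (SAP 11.4.1).

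If treatment alters such a variable, holding it fixed takes out the part of the effect that runs through it. If the variable also shares unmeasured causes with growth, holding it fixed adds a further distortion.

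Antibiotic use is the clearest case. Protocol Section 2 proposes that the product may interrupt a cycle that includes repeated infection. Re-hospitalisation for acute illness is an efficacy endpoint. Inclusion criterion 3 requires the antibiotic course to be finished before Day 1, and exclusion criterion 8 rules out ongoing infant antibiotics. Use during the study is therefore largely a marker of new illness, which the product is meant to affect.

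There is also a timing fault. The model fits Days 28, 56 and 90 together, so an antibiotic started after Day 28 becomes a covariate for the Day 28 outcome.

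At stake is the reading of the result. A true effect could look fragile, or the adjusted figure could be presented as the effect free of confounding. The SAP does not warn that the coefficient no longer estimates the total effect.

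**Working it through.** **The plan's own figure.** SAP 7.1.3 assumes a "difference in the WAZ change from baseline in 0.45 with a standard deviation of 1.3" and concludes, "using a 2-sided alpha of 5% and a power of at least 90%, a total of 354 participants, 177 in each group are required". With 1:1 allocation, n per arm = 2 × SD² × (z₀.₉₇₅ + z₀.₉₀)² / difference² = 2 × 1.69 × (1.960 + 1.282)² / 0.2025 ≈ 175.4, so 176 by the normal approximation. The noncentral t distribution gives 89.9% power at 176 and 90.1% at 177. The stated 177 is reproduced and is used below.

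**Formula.** In a linear model with one added covariate:

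adjusted effect = total effect − (arm difference in covariate) × (within-arm slope of outcome on covariate)

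If Bi-26 lowers antibiotic use by 10 points and use goes with 0.5 WAZ less growth, the product is (−0.10) × (−0.5) = 0.05, and 0.45 − 0.05 = 0.40. If the arm difference is zero, the product is zero and nothing shifts. If use were 10 points higher on Bi-26, the result would be 0.45 + 0.05 = 0.50, so the bias can run upward.

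**The rule as written.** The p<0.2 rule was applied in 4,000 simulated trials per scenario: 177 per arm, total effect 0.45, SD 1.3, and a Day 56 linear model as a simplification of the mixed model. The covariate is binary with 40% prevalence on placebo. Prevalence, arm differences and slopes are assumptions; the documents give none.

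| Arm difference (points) | Slope (WAZ) | By formula | Simulated mean | Covariate kept | Power |
|---|---|---|---|---|---|
| 10 | 0.5 | 0.45 − 0.05 = 0.40 | 0.400 | 98.7% | 83% |
| 20 | 0.5 | 0.45 − 0.10 = 0.35 | 0.349 | 97.6% | 71% |
| 20 | 1.0 | 0.45 − 0.20 = 0.25 | 0.251 | 100% | 48% |
| 30 | 1.0 | 0.45 − 0.30 = 0.15 | 0.150 | 100% | 20% |

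The unadjusted analysis had about 90% power throughout. The shares of 0.45 lost are 11%, 22%, 44% and 67%.

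**What the screen does.** A covariate unrelated to outcome entered in 19% of trials and left the mean at 0.45. With four independent unrelated candidates, the chance that at least one enters is 1 − 0.8⁴ = 59%. A covariate truly related to outcome was kept almost always. So the screen does not create the bias, but it does not prevent it either, and it leaves the final model to the data.

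**No true effect.** Take a covariate that treatment shifts and that shares a cause with growth, with within-arm correlation 0.3. The type I error of the adjusted test was 8% for an arm difference of 0.2 SD and 29% for 0.5 SD, against 5% unadjusted.

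**The case against.** The strongest reply is that this is a labelled sensitivity analysis. The primary model uses only baseline or design covariates, and Table 8 lists it on its own row. That stands: a reader might infer that the primary estimate is compromised, and the documents do not support that.

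A reader might also infer that adjustment could reverse the sign of the effect. At 0.45 this needs arm difference × slope above 0.45. For a binary covariate that is a slope above 0.45/0.20 = 2.25 WAZ at 20 points, or 0.45/0.30 = 1.5 WAZ at 30 points, against an outcome SD of 1.3. For a continuous covariate it is an arm difference above 0.45/(0.3 × 1.3) = 1.15 SD at correlation 0.3, or 0.49 SD at 0.7. Nothing in the documents suggests values of that size. Reversal becomes easy only when the true effect is small, where an estimate of either sign is near zero relative to a standard error of 1.3 × √(2/177) ≈ 0.14.

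Nor is bias certain. It requires an arm difference in the covariate. The trial is double-blind with matched placebo, and feeding counselling is the same in both arms. The protocol offers infection as a possible pathway, not an expected result, and says nothing of a change in breastmilk share. Place of storage is unlikely to respond to blinded treatment. The argument is strongest for antibiotic use and weaker for the rest.

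SAP 11.5.4.1 is a different case. It has no screen and tries to answer an endpoint defined by duration of dosing. It shares only the use of a post-randomisation covariate without a stated estimand.

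Finally, the primary estimand (Protocol Table 4, SAP Table 1) names feeding covariates that the primary model lacks. A reader might take the model in 11.5.2.4.2 as the one that matches the estimand. Table 8 does not say so, and a breastmilk share accumulated to Day 56 would not be a sound way to meet it.

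**Conclusion.** The concern holds in limited form. The listed variables cannot confound a randomised comparison. Where treatment affects one of them, the adjusted coefficient is biased for the total effect, usually by removing part of it, though either direction is possible. On moderate assumptions about antibiotic use, 0.45 becomes 0.40 to 0.35; stronger mediators leave less, and no arm difference leaves it unchanged. These sizes rest on assumed inputs and a single-visit simplification, so they show the mechanism and do not forecast this trial. The cause is the timing of the covariates; the p<0.2 rule and the open list add data-driven selection. The primary analysis stands. The sensitivity result as planned cannot validly confirm it or cast doubt on it.

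**What to change.** In SAP 11.5.2.4.2, replace the open list with a fixed set of baseline variables already in SAP 11.2: main type of feeding since birth, antibiotics in the 30 days before enrolment, sex, birth weight, and a refrigerator in the house. Enter them together. Drop the p<0.2 screen and the confounding label, and change the Table 8 row to match. The refrigerator item is the baseline substitute for storage, because dose storage is first recorded at Day 7 (Protocol Table 2).

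Keep compliance, breastmilk share and concomitant medication as the by-arm summaries already planned in SAP 11.4, 11.4.2 and 11.3. If an adherence effect is wanted, including for 11.5.4.1, define its estimand and use a randomisation-based method such as a complier-average effect.

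Cost: mainly SAP wording, with the same model code. Infants missing a baseline value such as birth weight would drop out of this model, with a slight loss of precision, so the SAP should say how they are handled. Only an adherence estimator would need new programming.
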